5.2 Subgroups/Stratification

There was no stratification in this study.

5.3 Time Windows

All data will be accepted for analysis. Deviations from the scheduled nominal visit days are not expected. Any deviations will be noted in the deviation log and visits may be considered for exclusion from the Per Protocol population.

5.4 Missing Data Handling

Missing data will not be imputed. All data available for dropouts will be considered in analyses.

6 Demographics and Baseline Characteristics

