4.5. Subject Replacement

Subjects who withdraw from the study post-randomization will not be replaced.

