9. STATISTICAL CONSIDERATIONS AND DATA ANALYSES

9.1 Sample Size Determination

Approximately 130 healthy females within the ages of 30 and 60 years with Fitzpatrick Skin Classification II-IV and moderate to advanced photo-damaged skin will be screened to randomize 80 subjects to ensure approximately 60 subjects (30 subjects per group) successfully complete the study. The sample size is based on clinical considerations and literature precedent [Narurkar, Schalka, Sulimovic, Kim].

With 30 subjects per treatment group, a change from baseline in TEWL at least half the magnitude of the standard deviation (CCI [REDACTED]) can be detected at two-sided alpha=0.05 with 80% power.

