	Combined (sum of) subject self-assessment scores for redness, pain, stinging/burning, itching, tightness and dryness
	Individual subject self-assessment scores for redness, pain, stinging/burning, itching, tightness and dryness
	Instrumental measurement of barrier function (Tewameter) and moisturisation (Corneometer)
Subject global self-assessment	
Assessment of skin recovery (change from baseline) between treatment groups.	All assessments and measurements listed above

3 Study Design

- Evaluator-blind

- Single study center
- Parallel-group
- Healthy female subjects with moderate to advanced photo-damaged facial skin
- Single test product (Physiogel Calming Relief SPF 20 Cream) used in combination with commercial sunscreen (“washout product”, Sunmax Sensitive SPF 50). All subjects were to use the commercial sunscreen and cleanser provided. Randomization was to two groups (test product, no test product) with product usage as shown in the table below:

Randomized Group	Morning	Lunchtime*	Evening
Group 1 (Test product)	1. Cleansing 2. Test Product 3. Sunscreen	1. Sunscreen	1. Cleansing 2. Test Product
Group 2 (No test product)	1. Cleansing 2. Sunscreen	1. Sunscreen	1. Cleansing

*Lunchtime application must be at least 3 hours after previous sunscreen application

4 Sample Size Determination

Approximately 130 healthy females within the ages of 30 and 60 years (inclusive) with Fitzpatrick Skin Classification II-IV and moderate to advanced photo-damaged skin will be screened to randomize 80 subjects to ensure approximately 60 subjects (30 subjects per group) successfully complete the study.

The sample size is based on clinical considerations and literature precedent [Narurkar, Schalka, Sulimovic, Kim]. With 30 subjects per treatment group, a change from baseline in Transepidermal Water Loss (TEWL) at least half the magnitude of the standard deviation (e.g. assume $std=4$ (ref. RH02030 after 2D strip), and 2.1 point mean change from baseline) can be detected at two-sided $\alpha=0.05$ with 80% power.

5 Data Considerations

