8.2 Secondary Analysis

Efficacy measurements in this study will be based on changes from baseline in TEWL and Corneometer values at each timepoint. Both measurements will be assessed pre-procedure and at Baseline (60±15 minutes post-procedure), 180 minutes post-procedure, 360 minutes post-procedure, and 1, 2, 3, 7 and 14 days post-procedure. The baseline for these measurements will be defined as the measurements made 60±15 minutes after the facial peel procedure, before any test product application.

Secondary assessments of local tolerance will be based on Evaluator (Dermatologist) and Subject self-assessment scores at each timepoint and reported adverse events. The baseline for these assessments will be defined as the assessments made 60±15 minutes after the facial peel procedure, before any test product application.

Evaluator and Subject assessment scores will be tabulated at each timepoint (Baseline (60±15 minutes post-procedure), 180 minutes post-procedure, and 1, 2, 3, 7 and 14 days post-procedure) for each product group descriptively as the number and percentage of subjects with each rating score for each assessment (none, mild, moderate or severe).

Changes from baseline in the Evaluator and Subject self-assessment and instrumental endpoints (TEWL and corneometry) will be tabulated by product group and timepoint and summarized descriptively using means, standard deviations and 95% confidence intervals and assessed for significance (different from zero) using t-tests or Wilcoxon signed rank tests dependent upon the distribution of the data.

Differences between product groups in the mean changes from baseline in Evaluator, and Subject self-assessment and instrumental endpoints will also be explored using t-tests or Wilcoxon rank sum tests at each timepoint and summarised using 95% confidence intervals.

If sufficient data is not available for formal analyses for individual scores, summary stats and frequency counts will be presented.

To visually inspect the treatment effect on subject self-assessment total scores, a plot

across time with the raw means will be produced. The plot will display a different symbol for each treatment group.

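### Day 7 and Day 14 recovery estimates ignore the earlier visits of subjects who have left, so they may be biased if leaving is related to skin response

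*SAP*

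**What the plan says.** Protocol 9.1 and SAP 4 plan "to randomize 80 subjects to ensure approximately 60 subjects (30 subjects per group) successfully complete the study". Protocol 4.5 adds: "Subjects who withdraw from the study post-randomization will not be replaced".

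On missing values, SAP 5.4 has two sentences: "Missing data will not be imputed", and "All data available for dropouts will be considered in analyses". Protocol 9.2.6 says the same.

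On method, SAP 8.2 summarises changes from the post-peel baseline by time point and tests them against zero within each arm by t-test or Wilcoxon signed rank test. Differences between arms "will also be explored using t-tests or Wilcoxon rank sum tests at each timepoint". Neither document gives a repeated-measures model or a missing-data sensitivity analysis.

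Under SAP 5.1, one post-baseline TEWL or corneometry value is enough to enter the ITT population, on which the efficacy analyses are based.

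**The concern.** A subject who leaves after the 72 h visit stays in the ITT population and contributes to the tests up to 72 h. She contributes nothing to the Day 7 and Day 14 estimates, although her baseline and early values are in the database and probably carry information about how she would have done. An available-case mean is unbiased for all treated subjects only if those who left resemble those who stayed.

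The late visits matter because the secondary objective is recovery over 14 days, and Protocol 3.4 justifies the length of the test phase by the need to follow desquamation and erythema. If leaving depends on early skin response, mean recovery within each arm can be misstated. The between-arm difference can also shrink, because an early product benefit makes the two arms lose different kinds and numbers of subjects.

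**Working it through.** **Inputs from the documents.** 80 randomised and about 60 completers (Protocol 9.1, SAP 4); no replacement (Protocol 4.5); no imputation (SAP 5.4); tests at each time point (SAP 8.2); TEWL SD of 4 "and 2.1 point mean change from baseline" (SAP 4). Equal allocation is implied by 30 completers per group but not stated.

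**The plan's own figures.** Implied allowance for loss: 1 − 60/80 = 25%. The power statement says the TEWL change "can be detected at two-sided alpha=0.05 with 80% power". For a one-sample t-test with n = 30, the noncentrality is (2.1/4) × √30 = 2.88 and the critical value on 29 df is 2.045, giving 79.4% (82.0% by normal approximation). The figure reproduces for change within an arm. A two-sample reading gives 51.6%, so the sample size speaks to the within-arm estimates.

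**Hand check of the within-arm effect.** If the d subjects (as a proportion) with the highest propensity to leave are lost, and propensity correlates r with poor late recovery, the mean of those remaining shifts by r × φ(z)/(1 − d), where z is the 1 − d normal quantile.
- d = 25%: φ(0.674)/0.75 = 0.424. For r = 0.3 and 0.5 the shift is 0.127 and 0.212 SD, or 0.51 and 0.85 TEWL points at SD 4.
- d = 5%: φ(1.645)/0.95 = 0.109. The shift is 0.033 and 0.054 SD, or 0.13 and 0.22 points.
- r = 0: no shift.

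**Simulation.** Every setting here is an assumption. Visits at 24, 48, 72, 168 and 336 h; unit SD; equal correlation r between visits; higher values worse; product benefit 0.50 SD at 24 to 72 h, 0.35 at Day 7 and 0.20 at Day 14. The log-odds of leaving before Day 14 rise by b per SD of a worse 72 h value, with the intercept set for 25% loss overall. Samples are very large, so the results show bias rather than noise.

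| r | b | Day 14 difference, available case (true 0.20) | Within-arm recovery overstated by (SD) |
|---|---|---|---|
| 0.3 | 0.5 | 0.19 | 0.03 to 0.04 |
| 0.3 | 1.0 | 0.18 | 0.06 to 0.07 |
| 0.3 | 1.5 | 0.17 | 0.07 to 0.10 |
| 0.6 | 0.5 | 0.19 | 0.07 to 0.08 |
| 0.6 | 1.0 | 0.16 | 0.11 to 0.15 |
| 0.6 | 1.5 | 0.14 | 0.14 to 0.20 |

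The two values in the last column are the test arm and the no-product arm. An estimate that also uses the 24 to 72 h values returns 0.20 throughout.

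**Variations.**
- b = 0 (leaving unrelated to skin): no bias.
- b = −1 (better-recovering subjects leave), r = 0.6: within-arm recovery is understated by 0.11 to 0.15 SD. The between-arm difference is still too small, at about 0.16 to 0.17.
- 5% loss, same r and positive b: difference 0.18 to 0.20; within-arm bias at most 0.05 SD.

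**Scale.** With 30 completers per arm, the standard error of a between-arm difference is √(2/30) = 0.26 SD. The largest between-arm bias above, 0.20 − 0.14 = 0.06 SD, is 0.06/0.26 = 0.23 of that. The within-arm standard error is 1/√30 = 0.18 SD, so the within-arm bias runs from 0.03/0.18 = 0.17 to 0.20/0.18 = 1.1 standard errors. At a TEWL SD of 4 it is 0.12 to 0.80 points, or 6% to 38% of the 2.1-point change used for power.

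**The case against.** The strongest opposing case has five parts.

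First, a reader might infer that SAP 5.4 is contradicted. It is not. A dropout enters every test at each visit she attended, and no data exist after she leaves. The gap is only that her earlier values do not inform later time points.

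Second, a reader might infer that late recovery is in fact estimated in the subjects who healed better. The documents do not show this. The peel is classed as superficial (Protocol 1), subjects with a severe forearm reaction are discharged before randomisation (Protocol 6.1.11, 6.2.8, 6.3.8), and the withdrawal reasons in Protocol 6.8.14 include non-medical ones. The bias could be nil or reversed. Skin-related loss is nevertheless plausible: a severe skin score counts as an adverse event (Protocol 6.4.2), adverse event is a listed withdrawal reason, and in the retinoic acid peel study cited in Protocol 3.4 one of the two losses was for contact dermatitis in the test arm.

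Third, 25% is a planning allowance and not a stated expected rate. That peel study lost 2 of 52 (3.8%) in one week, and at about that level the effect is small.

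Fourth, these analyses are secondary and the between-arm tests exploratory. Success rests on the global tolerance assessment, whose table (SAP Table 9.3.1) has a row for missing values and percentages based on all subjects in the group. TEWL is expected to normalise by 24 to 48 h (Protocol 3.4), and the templates already show numbers missing by arm and time point.

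Fifth, the remedy is not free. The total scores are sums of 0 to 3 ordinal items, may cluster at zero late on, and have a Wilcoxon option that a Gaussian model would displace.

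All five stand as limits on the point. None removes the fact that data already collected go unused for the late estimates. The simulation does favour the model, since leaving depends only on an observed value. If leaving depends on unobserved skin state, the model reduces the bias only in part.

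**Conclusion.** The point holds in conditional form. The Day 7 and Day 14 estimates are available-case estimates under a plan that tolerates up to 25% loss, and they may be biased if leaving is related to earlier skin response. Under the stated assumptions, the Day 14 between-arm difference is about 0.14 to 0.19 SD against a true 0.20, well inside one standard error. Within-arm recovery is overstated by about 0.03 to 0.20 SD, which at the upper end is about one standard error. The direction of the within-arm bias depends on who leaves, and its size on how many.

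The correlations, the mechanism of leaving and the benefit profile are assumptions; the documents give none of them. The primary tolerance result is outside this point.

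**What to change.** In SAP 8.2, for TEWL and Corneometer, make the main estimate a mixed model for repeated measures on change from baseline. Include arm, time, arm × time and baseline × time, with an unstructured covariance and a named simpler structure to use if it does not converge. Report within-arm least-squares mean changes and between-arm differences with 95% confidence intervals at each time point. Keep the per-time-point tests as supportive.

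For the dermatologist and subject total scores, keep the planned t or Wilcoxon tests as the main analysis and add the same model as supportive.

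The model imputes nothing, so SAP 5.4 can stand. SAP 12, which reports no change to the protocol-planned analyses, should record the addition before unblinding.

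The cost is SAP wording and modest programming. The main technical burden is the covariance: the instruments have seven post-baseline time points (180 and 360 minutes; Days 1, 2, 3, 7 and 14), so an unstructured matrix has 7 × 8/2 = 28 parameters in about 80 subjects. That is why the fallback must be named in advance. If loss proves low or unrelated to skin, the results should differ little from the planned ones, apart from some gain in precision.

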6.1 Subject Disposition

The number of overall subjects screened and who screen failed will be presented with the number and percentage of subjects randomized and completing the study by product group.

The number and percentage of subjects, in the Safety, ITT and PP populations will be presented by product group and overall. The percentages will be based upon the total number of subjects randomized.

The number and percentage of subjects completing the study and not completing the study, including a breakdown of the reasons for not completing the study, will be presented by product group and overall. The percentages will be based upon the total number of subjects randomized

6.2 Demographics

Age will be summarized descriptively for each product group using means, medians and standard deviations. Race, gender, Fitzpatrick phototype and Glogau photoaging type will be summarized by product group using frequency counts and percentages.

7 Treatment Compliance and Concomitant Medications

7.1 Treatment Compliance

Treatment compliance (application of either the test product or sunscreen) will be assessed during the blinded data review meeting and a listing will be produced for evaluation of protocol violations only. No formal listing of these data will be produced for the study report.

7.2 Concomitant Medications

Concomitant medications and concomitant non-drug treatment procedures will be assessed during the blinded data review meeting and a listing will be produced for evaluation of protocol violations only. No formal listing of these data will be produced for the study report.

8 Analysis

8.1 Primary Analysis

The primary evaluation of tolerance will be based on the Evaluator (Dermatologist) global assessment. The trial will be considered a success if the majority of subjects in the test product group have a favorable (“well tolerated”) Evaluator global assessment score.

The Dermatologist will assess the local tolerance of the post-procedure skin care regimen in context of the expected effects of the procedure for each subject using the scale below and document the score on the eCRF. To make this assessment, the Dermatologist will draw on the total set of clinical and subject self-assessment data for each subject. The Dermatologist must be unaware of whether a subject was randomized to test product to protect the blind.

Rating	Description
0 - Product Regimen was Well Tolerated	No clinically significant worsening of the expected signs/symptoms of the procedure. No new signs/symptoms manifest during product use.
1 - Product Regimen was Not Well Tolerated	Clear, clinically relevant worsening of the severity or frequency of expected signs/symptoms of the procedure and/or any occurrence of new, unexpected signs/symptoms during product use.

Descriptive statistics (N, percentage, 95% confidence intervals) will be used to summarize the proportion of subjects in each product group with a favorable Evaluator global assessment of tolerance. The proportions will also be compared between product groups using Chi-square test, and difference in proportion and 95% confidence interval.

To visually inspect the treatment effect on dermatologist total score, a plot across time with the raw means will be produced. The plot will display a different symbol for each treatment group.

8.2 Secondary Analysis

Efficacy measurements in this study will be based on changes from baseline in TEWL and Corneometer values at each timepoint. Both measurements will be assessed pre-procedure and at Baseline (60±15 minutes post-procedure), 180 minutes post-procedure, 360 minutes post-procedure, and 1, 2, 3, 7 and 14 days post-procedure. The baseline for these measurements will be defined as the measurements made 60±15 minutes after the facial peel procedure, before any test product application.

Secondary assessments of local tolerance will be based on Evaluator (Dermatologist) and Subject self-assessment scores at each timepoint and reported adverse events. The baseline for these assessments will be defined as the assessments made 60±15 minutes after the facial peel procedure, before any test product application.

Evaluator and Subject assessment scores will be tabulated at each timepoint (Baseline (60±15 minutes post-procedure), 180 minutes post-procedure, and 1, 2, 3, 7 and 14 days post-procedure) for each product group descriptively as the number and percentage of subjects with each rating score for each assessment (none, mild, moderate or severe).

Changes from baseline in the Evaluator and Subject self-assessment and instrumental endpoints (TEWL and corneometry) will be tabulated by product group and timepoint and summarized descriptively using means, standard deviations and 95% confidence intervals and assessed for significance (different from zero) using t-tests or Wilcoxon signed rank tests dependent upon the distribution of the data.

Differences between product groups in the mean changes from baseline in Evaluator, and Subject self-assessment and instrumental endpoints will also be explored using t-tests or Wilcoxon rank sum tests at each timepoint and summarised using 95% confidence intervals.

If sufficient data is not available for formal analyses for individual scores, summary stats and frequency counts will be presented.

To visually inspect the treatment effect on subject self-assessment total scores, a plot

across time with the raw means will be produced. The plot will display a different symbol for each treatment group.

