2. OBJECTIVE(S) AND ENDPOINT(S)

Objective(s)	Endpoint(s)
Primary	
Assessment of the local tolerance of the test product in subjects who have undergone a 70% Glycolic Acid facial peel	Evaluator (Dermatologist) global assessment of tolerance
Secondary	
Assessment of skin recovery (change from baseline) over a period of 14 days in subjects who have undergone a 70% Glycolic Acid facial peel	
Combined (sum of) Evaluator (Dermatologist) scores for signs/symptoms of erythema, edema, desquamation and dryness
 
Individual Evaluator (Dermatologist) scores for erythema, edema, desquamation and dryness
 
Combined (sum of) subject self-assessment scores for redness, pain, stinging/burning, itching, tightness and dryness
 
Individual subject self-assessment scores for redness, pain, stinging/burning, itching, tightness and dryness
 
Instrumental measurement of barrier function (Tewameter) and moisturisation (Corneometer)
 
Subject global self-assessment

Assessment of skin recovery (change from baseline) between treatment groups.	All assessments and measurements listed above

 GlaxoSmithKline	Document Name	GSK267237/21308F 20 Day Cream.doc		
	Type	Version	Document Identifier	Effective Date
	eldo_controlled	0.0: Current Effective/Current	090032d580e2d816	07-Jun-2017 01:32:30
	Reason For Issue	Auto Issue		

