Schalka (2013) published the results of a clinical study which investigated the efficacy and safety of a novel cosmetic skin care product in subjects who underwent a 5% retinoic acid facial peel. This comparative, open-label clinical study randomized 52 subjects who were divided into two groups, with 26 subjects allocated to each group. One group was provided with a Sun Protection Factor (SPF) 30 cream (control) and the other group was provided with the test product and SPF 30 control. Regular clinical assessment and biophysical measurements were conducted for a

 GlaxoSmithKline	Document Name	090032d580e2d8a6 20 Day Cream.doc		
	Type	Version	Document Identifier	Effective Date
	eldo_controlled	0.0; Current Effective	090032d580e2d8a6	07-Jun-2017 01:32:30
	Reason For Issue	Auto Issue		

period of 1 week post-procedure. Fifty subjects completed the study, with one subject withdrawing for personal reasons and the other discontinued from the study due to the occurrence of mild contact dermatitis in the test product plus sunscreen group. Statistically significant ($p \leq 0.05$) cosmetic benefits were observed for clinically-assessed desquamation (Days 4 to 7) and instrumental Corneometer measurements (Days 2 to 4) for the treatment group over the control group. Crucially, the magnitude of cosmetic assessments between groups was numerically largest between days 2 and 4, presumably because the skin's natural repair processes were continually reducing the cutaneous damage for both groups, making it more difficult to measure a cosmetic benefit over time. Barrier function was observed to gradually worsen over the duration of the study, with weak indications of improvement between days 4 and 7. There was no statistically significant barrier function benefit between groups at any time point.

Based on this literature review, subject visits have been included at 24-72 hours post-procedure, where differences between control and test groups are expected to be largest. While it is expected the skin's barrier function will return to normal 24 to 48 hours following the procedure, the total duration of the test phase is 14 days to enable sufficient time to monitor desquamation and erythema compared to the post-procedure, pre-treatment baseline.

 GlaxoSmithKline	Document Name	GSK-207237-01-001F 20 Day Cream.doc		
	Type	Version	Document Identifier	Effective Date
	eldo_controlled	0.0: Current Effective/Current	090032d580e2d8a6	07-Jun-2017 01:32:30

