9.3.3. Secondary Analysis(es)

Changes from baseline in the Evaluator, Subject self-assessment and instrumental endpoints will be tabulated by product group and summarized descriptively using means, standard deviations and 95% confidence intervals and assessed for significance (different from zero) using t-tests or Wilcoxon signed rank tests dependent upon the distribution of the data.

 GlaxoSmithKline	Document Name	GSK267237/21308F 20 Day Cream.doc		
	Type	Version	Document Identifier	Effective Date
	eldo controlled	0.0; Current Effective Date: 07-Jun-2017 01:32:30	090032d580e2d8a6	07-Jun-2017 01:32:30
	Reason For Issue	Auto Issue		

Differences between product groups in the mean changes from baseline in Evaluator, Subject self-assessment and instrumental endpoints will also be explored using t-tests or Wilcoxon rank sum tests and summarised using 95% confidence intervals.

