Product Regimen was Well Tolerated	XX (XX%)	XX (XX%)
Product Regimen was Not Well Tolerated	XX (XX%)	XX (XX%)
95% Confidence Interval for Proportion Well Tolerated	(XX.X%, XX.X%)	(XX.X%, XX.X%)
Difference in Proportions Well Tolerated (95% Confidence Interval)		XX% (XX.X - XX.X)
Chi-Square P-Value		X.XXX

Percentages based on the total number of subjects per product group.

Program file name xxxxxxxxxxxxxxxxxxxxxx

Table 9.3.3.2.1
 Summary of Dermatologist Assessments - Total Score[®]- Changes from Baseline
 Safety Population

Safety Population (N=xx)

Timepoint		Physiogel Calming Relief	No Test Product
		SPF 20 Cream	
Pre-Procedure Assessment	N	XX	XX
	Missing	XX	XX
	Mean	X.XX	X.XX
	SD	X.XXX	X.XXX
	95%CI	X.XX, X.XX	X.XX, X.XX
Baseline*	N	XX	XX
	Missing	XX	XX
	Mean	X.XX	X.XX
	SD	X.XXX	X.XXX
	95%CI	X.XX, X.XX	X.XX, X.XX
180 Minutes Post-Procedure	N	XX	XX
	Missing	XX	XX
	Mean	X.XX	X.XX
	SD	X.XXX	X.XXX
	95%CI	X.XX, X.XX	X.XX, X.XX
Change from Baseline at 180 Minutes	N	XX	XX
	Missing	XX	XX
	Mean	X.XX	X.XX
	SD	X.XXX	X.XXX
	95%CI	X.XX, X.XX	X.XX, X.XX

	P-Value [‡]	X.XXX	X.XXX
Difference between Groups at	Difference	X.XX (X.XX, X.XX)	
180 Minutes	(95%CI)		
	P-Value [§]	X.XXX	
...		...	

[‡] Total score=sum of Erythema, Dryness, Desquamation/Peeling and Edema individual scores.

[‡] P-value from t-test or Wilcoxon signed rank test compared to zero.

[§] P-value from t-test or Wilcoxon rank sum test.

* Baseline score is assessed 60 minutes post-procedure and prior to any test product application.

Program file name xxxxxxxxxxxxxxxxxxxxxx

Programmers Note: Continue table for each timepoint. Same format for Tables 9.3.2.2.x, 9.3.3.2.x, 9.3.4 and 9.3.5 - Change the title, footnote and timepoints to match protocol.

7 Days

14 Days

Desquamation

Pre-procedure	X(xx%)	X(xx%)	X(xx%)	X(xx%)	X(xx%)	X	X(xx%)	X(xx%)	X(xx%)	X(xx%)	X(xx%)	X
Baseline* Score	X(xx%)	X(xx%)	X(xx%)	X(xx%)	X(xx%)	X	X(xx%)	X(xx%)	X(xx%)	X(xx%)	X(xx%)	X
180 Min	X(xx%)	X(xx%)	X(xx%)	X(xx%)	X(xx%)	X	X(xx%)	X(xx%)	X(xx%)	X(xx%)	X(xx%)	X
1 Day	X(xx%)	X(xx%)	X(xx%)	X(xx%)	X(xx%)	X	X(xx%)	X(xx%)	X(xx%)	X(xx%)	X(xx%)	X
2 Days	X(xx%)	X(xx%)	X(xx%)	X(xx%)	X(xx%)	X	X(xx%)	X(xx%)	X(xx%)	X(xx%)	X(xx%)	X
3 Days	X (xx%)	X (xx%)	X (xx%)	X(xx%)	X(xx%)	X	X (xx%)	X(xx%)	X(xx%)	X(xx%)	X(xx%)	X
7 Days	X (xx%)	X (xx%)	X (xx%)	X(xx%)	X(xx%)	X	X (xx%)	X(xx%)	X(xx%)	X(xx%)	X(xx%)	X
14 Days	X (xx%)	X (xx%)	X (xx%)	X(xx%)	X(xx%)	X	X (xx%)	X(xx%)	X(xx%)	X(xx%)	X(xx%)	X

Edema

Pre-procedure

Baseline* Score

180 Min

1 Day

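### Between-group recovery is tested on unadjusted change from the 60-minute baseline; using that baseline as a covariate would generally give tighter estimates from the same data

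*SAP*

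**What the plan says.** Protocol section 2 lists "Assessment of skin recovery (change from baseline) between treatment groups" as a secondary objective. For the analysis, Protocol 9.3.3 says group differences in mean change "will also be explored using t-tests or Wilcoxon rank sum tests and summarised using 95% confidence intervals". SAP 8.2 repeats this for each time point: "Differences between product groups in the mean changes from baseline in Evaluator, and Subject self-assessment and instrumental endpoints will also be explored using t-tests", with the rank sum test as the alternative. The template for SAP Table 9.3.3.2.1, which also serves the TEWL, Corneometer and self-assessment change tables, footnotes the between-group result as "P-value from t-test or Wilcoxon rank sum test".

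Baseline is the value taken 60±15 minutes after the peel and before any test product. For TEWL and Corneometer there is an earlier value too: "Both measurements will be assessed pre-procedure and at Baseline". Neither document contains an ANCOVA, a regression or a mixed model. SAP section 12 reports no change to the protocol's analyses beyond the population definitions.

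**The concern.** A test on raw change assumes that each extra unit of TEWL at 60 minutes carries forward as one extra unit at follow-up. The protocol's own expectation makes that doubtful. Section 3.4 anticipates that the skin's "barrier function will return to normal 24 to 48 hours following the procedure". If so, later TEWL may depend only weakly on how damaged the skin was at 60 minutes, and subtracting the whole baseline adds its variation to the outcome.

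There is a second effect. SAP 5.2 confirms that randomisation was not stratified. If one arm happens to start with more post-peel damage, the unadjusted estimate moves with that imbalance. It is unbiased over repeated randomisations, but not conditionally on the imbalance observed.

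At stake is the width of the intervals for a listed objective. The 24 to 72 hour visits were placed where "differences between control and test groups are expected to be largest", and the TEWL and Corneometer change tables are part of the topline summary.

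**Working it through.** **Inputs from the documents.** SAP section 4 gives 30 completers per group, SD 4, "and 2.1 point mean change from baseline", two-sided alpha 0.05 and 80% power. Forty per arm is the 80 randomised split equally.

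**Assumed, because the documents do not give them.** SD 4 is the SD of change. The correlation rho between baseline and follow-up is 0.3, 0.5 or 0.7. The ratio lam = follow-up SD / baseline SD is 1 unless stated.

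**The plan's own figure.** A one-sample t-test of a change of 2.1 with SD 4 and n = 30 has power 79.4% (noncentral t), which matches the stated 80%. The sample size statement is therefore a within-group calculation and gives no between-group target.

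**Variance ratio, ANCOVA to change score.**

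ratio = lam²(1 − rho²) / (1 + lam² − 2·rho·lam)

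At lam = 1 this is (1 + rho)/2, that is 0.65, 0.75 and 0.85. A simulation at 30 per arm gave 0.67, 0.78 and 0.86. The small excess is the price of estimating the slope, a factor (N − 3)/(N − 4): 57/56 = 1.018 at N = 60 and 77/76 = 1.013 at N = 80.

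**Half-widths and power.**

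- Unadjusted: SE = 4·√(2/n), df = N − 2. At n = 30, SE = 1.033 and the half-width is 2.002 × 1.033 = 2.07.
- ANCOVA: SE = 4·√(ratio × cost × 2/n), df = N − 3. At n = 30 and rho 0.5, SE = 4·√(0.75 × 1.018 × 2/30) = 0.902 and the half-width is 1.81.

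The power columns take 2.1 as a true group difference. This borrows the within-group figure for illustration; the documents propose no such group difference.

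| Analysis | Half-width, 30/arm | Half-width, 40/arm | Power for 2.1, 30/arm | Power for 2.1, 40/arm |
|---|---|---|---|---|
| Change score | 2.07 | 1.78 | 51.6% | 64.0% |
| ANCOVA, rho 0.3 | 1.68 | 1.45 | 69% | 82% |
| ANCOVA, rho 0.5 | 1.81 | 1.55 | 63% | 76% |
| ANCOVA, rho 0.7 | 1.92 | 1.65 | 58% | 71% |

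**Chance imbalance.** At lam = 1 the baseline SD is 4/√(2(1 − rho)). A one-standard-error baseline difference between arms then shifts the change-score estimate by 4·√((1 − rho)/30) = 0.61, 0.52 or 0.40 units.

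**Unequal variances, 30 per arm.**

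| lam | Ratio at rho 0.3 / 0.5 / 0.7 | After slope cost |
|---|---|---|
| 0.75 | 0.46 / 0.52 / 0.56 | 0.47 / 0.53 / 0.57 |
| 1.5 | 0.87 / 0.96 / 1.00 | 0.89 / 0.98 / 1.02 |

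The ratio reaches 1 when rho × lam = 1, for example lam = 2 with rho 0.5. There ANCOVA gains nothing and costs about 1.8% of variance.

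**The case against.** The strongest reply is that this is a preference and not a defect. The planned test is unbiased, the group comparison is described as exploratory, and success rests on the global tolerance rating, which has no baseline. All of that stands and sets the weight of the point.

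The size of the gain is also uncertain. Section 3.4 cites a retinoic acid peel study in which barrier function gradually worsened over the week. Returning to one's own normal does not by itself imply a low correlation either, because stable differences between women can be present at both times. SD 4 comes from a tape-strip reference and might be the SD of a single reading. In that case the half-width at 30 per arm would go from 2.45, 2.07 and 1.60 to 1.99, 1.81 and 1.49 for rho 0.3, 0.5 and 0.7. These points change the amount, not the direction, except where the slope is close to 1.

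The total scores are sums of 0 to 3 items and bounded at zero, so a linear model fits them less comfortably than TEWL. Keeping the rank test alongside answers this in part.

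The baseline is measured after randomisation. It nevertheless precedes product dispensing and application, and the dermatologist giving the peel is blind to allocation, so it serves as a pre-treatment covariate. The tables already show baseline means by group, which makes an imbalance visible but does not correct for it.

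**Conclusion.** The point holds as an optional improvement in precision. The plan compares groups on raw change with no covariate, which is generally less precise than adjusting for the 60-minute value. For TEWL at 30 per arm, the interval half-width would fall by about 0.15 to 0.39 units from 2.07. This assumes an SD of change of 4, equal variances and a correlation between 0.3 and 0.7. The gain is larger if follow-up values vary less than baseline values, and close to nil if they vary much more. The downside is about 1.8% of variance, incurred when the true slope is near 1, so that baseline is uninformative about the change. A baseline that does not predict follow-up is a different case and favours ANCOVA strongly (ratio 0.50 at rho 0 with equal variances). The figures do not carry over to the Corneometer or the scores. The primary endpoint and the success rule are unaffected.

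**What to change.** In SAP 8.2, estimate the group difference in TEWL, Corneometer and the two total scores by ANCOVA at each time point, with the 60-minute baseline as covariate. One repeated-measures model with a group-by-time term would also serve. Add the pre-procedure value as a second covariate for the two instrumental endpoints only; its benefit has not been quantified here. Report adjusted differences with 95% confidence intervals in Tables 9.3.2.2.1, 9.3.3.2.1, 9.3.4 and 9.3.5. Keep the planned t-test or Wilcoxon rank sum test as a sensitivity analysis, and leave the individual 0 to 3 scores as planned.

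Record the change in SAP section 12 as a departure from Protocol 9.3.3, before unblinding. If unblinding has already happened, label the adjusted analysis post hoc.

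The cost is SAP wording, table shells and programming, and one degree of freedom per covariate. A covariate that adds no information costs up to about 1.8% of variance at 30 per arm or 1.3% at 40. No new data are needed.
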